### 8.3 Applicable significance level

Analysis will be performed in a descriptive manner, so, there will be no applicable statistical tests. However, 95% confidence intervals will be calculated for means and proportions, so, 95% significance level will be applied that corresponds to 5% alpha (type I) error.

As there are no statistical tests applied to any of the tabulated data, there will be no multiplicity (multiple comparison) corrections applied to the significance level.

### 8.4 Handling of missing or incorrect data

Assigned data manager and statistician will continuously identify missing, questionable or non-interpretable data in the study database, and queries will be generated to study sites to address this.

All missing, questionable or non-interpretable data that were not clarified through query generation process will be treated as missing and not included in the final statistical database for interim and final analyses. Listing of such data will be provided as an attachment to the statistical analysis report, if applicable.

Protocol ID	MACS-2017-102279	STATISTICAL ANALYSIS PLAN	Page 29 of 41	
IP	N/A		Date	30.12.2021
ID	MACS-2017-102279_SAP		Version	v1.2 final

Missing data will not be restored. No procedures for missing data pattern assessment and/or imputation are planned.

### **8.5 Procedures for reporting of any deviations from the initial statistical analysis plan**

Any decision to change statistical analysis plan that will contradict the protocol, should be approved by study Sponsor. Final study report should contain all changes made compared to the original statistical analysis plan with the appropriate justification of such changes.

### **8.6 Analysis populations (data sets)**

Due to observational nature of this study patients will not be excluded from analysis based on their performance and/or data availability. All obtained data will be summarized after data base cleaning and lock.

All planned analyses (including descriptive analyses and study listings) will be performed for Full Analysis Set (FAS) of data.

The following patient's populations will be included into statistical analysis:

- **All Patients Enrolled population (equal to FAS):** All patients who signed informed consent to enter the study.

*Subjects that were enrolled with the violation of inclusion and subsequently withdrawn from the study (upon recognition of such violation) will be excluded from FAS and analyzed separately for baseline characteristics only (the decision whether to analyze such patients in the interim analysis will be defined by the number of such patients – summary data will be presented if this subgroup is >10 observations).*

- **Safety population:** Patients who have taken at least one dose of any IBD medicine after enrolling in the study (Baseline visit).

Due to observational nature of the study, and possible presence of missing data for analysis, it is possible to exclude several patients or the entire study center at the analysis stage.

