15.2.2. Statistical analysis methods

All data from patients enrolled in this study will be analyzed. Information on CD and UC patients will be presented separately. Also, analysis will be performed separately by therapy subgroups (patients receiving non-biological therapy and patients receiving biological therapy). Due to complexity of treatment regimen a manual review can be used to define treatment subgroup for each patient.

A descriptive analysis approach will be used to analyze the data and the study outcomes for the different study subgroups.

Descriptive statistics will include summary tables (n, mean, median, standard deviation, minimum and maximum, lower and upper quartile for continuous variables and n, frequency and percentage for categorical values). Proportion will be assessed together with 95% confidence interval, if applicable. Cross tabulations will be used to present study outcomes by the corresponding subgroups, when required. Time to event will be described with Kaplan-Meier estimates. Median time to event will be presented together with the lower and upper quartiles. Baseline and retrospective data will be used to describe the patient population and will be tabulated separately.

The number and percentage of patients who have reached remission while in the study will be presented. Selected outcomes will be reported separately for those who have reached remission and those who haven't.

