15.2.4. Potential study biases

The study limitations are those inherent to uncontrolled observational studies. Taking into account observational and uncontrolled nature of the study, fully evaluating of non-biological /biological treatment effectiveness will not be available. However, data regarding in real-life practice will be gathered and analyzed. The inclusion criteria are those that used when administering non-biological /biological treatment in practice and therefore, the same criteria as those that would have been used if we had performed a similar prospective study. This type of experimental design should prevent selection bias that could occur when patient enrollment is related to the development of the outcome. In prospective observational study like this attrition bias is possible, however, in case of early leaving study last data will be gathered and effectiveness will be estimated, these cases will not be excluded from effectiveness analysis.

Details of the statistical analyses will be presented in the Statistical Analysis Plan.

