In all cases, the reason for withdrawal must be recorded in the eCRF and in the patient's medical records. The patients who prematurely withdrew from the study are not replaced with new ones, and their data will be included into the final analysis. In case if investigator loses contact with the patient during the study observation, the investigator may contact with the patient directly or through the other health care professionals who observe this patient in routine practice. In that case part of eCRF "End of observation" can be filled based on data received via e-mails/calls.

Protocol ID	MACS-2017-102279	STATISTICAL ANALYSIS PLAN	Page 15 of 41	
IP	N/A		Date	30.12.2021
ID	MACS-2017-102279_SAP		Version	v1.2 final

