final analysis, will be performed using the updated MedDRA versions and all previously analyzed data will be checked using MedDRA version comparison tool for the presence of changes from version to version and re-coded if applicable. The updated version of MedDRA used in the final analysis will be specified in the SAR. Both original and updated coding will be kept for tracking purposes.

Concomitant and prior medications will be coded with Anatomical Therapeutic Chemical Dictionary (ATC) current version.

Due to the descriptive nature of the study, all available data will be analyzed.

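### SAP 8.6 rules out exclusion for data availability, then lets patients or a whole centre be dropped for missing data, with no criterion or limit

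*SAP*

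**What the plan says.** SAP 8.6 contains both rules. At its start: "patients will not be excluded from analysis based on their performance and/or data availability". It then says that all planned analyses use the Full Analysis Set, defined as everyone who signed consent. It closes by appealing to the observational nature of the study and possible missing data: "it is possible to exclude several patients or the entire study center at the analysis stage". Between the two is one defined exclusion, for patients enrolled in violation of the inclusion criteria and later withdrawn. That exclusion has a stated rule and is not at issue here.

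Other statements on who is analysed:

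- Protocol 15.1 has the same bar as the opening of SAP 8.6 and no permission to exclude.
- Protocol 15.2.2: "All data from patients enrolled in this study will be analyzed".
- SAP 8.1.1: "Due to the descriptive nature of the study, all available data will be analyzed".
- For early leavers, SAP 5.4.2 and Protocol 11.5.3 state that "their data will be included into the final analysis", and Protocol 15.2.4 that "these cases will not be excluded from effectiveness analysis".
- SAP 8.4 says that items left unresolved after queries "will be treated as missing and not included in the final statistical database for interim and final analyses". It also rules out imputation and any assessment of the missing-data pattern.
- SAP 8.5: "Any decision to change statistical analysis plan that will contradict the protocol, should be approved by study Sponsor".

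**The concern.** The two rules in SAP 8.6 rest on the same ground, the observational nature of the study, and cannot both hold. An analyst who drops a site with poor follow-up and one who keeps it can each cite this section.

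In a descriptive study with no hypothesis test, the analysis set largely determines the result. The open permission reaches the treatment-pattern distributions and the failure percentages alike. Nothing requires the choice to be made before results are seen, and no confidence interval reflects it. Protocol 11.4 requires consecutive enrolment to limit selection bias; discretionary removal at analysis could bring that bias back. Because the missing-data pattern will not be assessed, no planned check would show whether the excluded patients differ from those kept.

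**Working it through.** **Is the permission governed elsewhere?** The rules that come closest do other jobs:

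| Place | What it governs |
|---|---|
| SAP 8.6, inclusion violators | Eligibility; the more-than-10 figure concerns reporting |
| SAP 8.4 | Individual unresolved items, not patients or centres |
| SAP 8.7 | eCRF completeness for interim analyses |
| SAP 8.1.2 | Treatment combinations seen in fewer than 25 subjects |
| Protocol 11.3 and 14.3.2 | Data without signed consent |
| SAP 8.5; Protocol 15.2.1 flow diagram | Approval of plan changes; disclosure |

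None gives a criterion for excluding a patient or centre because data are missing.

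**Is the permission needed?** No. Under SAP 8.4 an unresolved item becomes missing. Percentages already use non-missing observations (Protocol 15.2.1, SAP 8.1.1), and tables show population size including missing observations (SAP 8.1.4).

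**How much could it matter?** The documents do not say how many patients might be excluded, so this is illustrative. The group is Crohn's disease patients on biologics, for whom Protocol 15.4 states its precision.

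*Inputs from Protocol 15.4:* 2000 enrolled, 40% on biologics, 40% Crohn's disease, 10% drop-out, failure rate 40% or 50%. *Number of sites:* about 35 (Protocol 7.2).

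*The plan's own figure.* n = 2000 × 0.40 × 0.40 × 0.90 = 288. Half-width = 1.96 × √(p(1−p)/n):

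- p = 0.50: 1.96 × √(0.25/288) = 5.77 points, giving 44.2–55.8%, as stated.
- p = 0.40: 1.96 × √(0.24/288) = 5.66 points, giving 34.3–45.7%, as stated.

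Expected failures are 144 at 50% and 115.2 at 40%.

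*One average site.* 288/35 ≈ 8 patients, leaving 280. The extremes are that all 8 are non-failures or all 8 are failures:

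- At 50%: 144/280 = 51.4% or 136/280 = 48.6%, a shift of ±1.4 points.
- At 40%: 115.2/280 = 41.1% or 107.2/280 = 38.3%, a shift of +1.1 or −1.7 points.

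*Several patients, taken as 5, all failures.*

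- At 50%: 139/283 = 49.1%, a shift of −0.9 points.
- At 40%: 110.2/283 = 38.9%, a shift of −1.1 points.

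*A large atypical centre (assumed).* With 10% of the group (28.8 patients) and failure rate q, the remaining rate is (failures − 28.8q)/259.2:

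| Overall rate | q = 0.2 | q = 0.8 |
|---|---|---|
| 50% | 53.3% (+3.3) | 46.7% (−3.3) |
| 40% | 42.2% (+2.2) | 35.6% (−4.4) |

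With 20% of the group (57.6 patients) and an overall rate of 50%, (144 − 57.6q)/230.4 gives 57.5% or 42.5%. That shift of 7.5 points exceeds the planned half-width.

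*Failures only.* The number x that must be removed to move the estimate by the full half-width is x = (f − 288t)/(1 − t), where f is the number of failures and t = p − half-width.

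- At 50%: x = 29.8, so 30 of 288 (10.4%); check 114/258 = 44.2%.
- At 40%: x = 24.8, so 25 of 288 (8.7%); check 90.2/263 = 34.3%.

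*Precision.* Losing one average site widens the half-width at 50% only from 5.77 to 5.86 points, so the issue is selection rather than sample size.

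**The case against.** The clause is not wholly unbounded. It names a ground (missing data) and a rough scale. Used as worded, its effect is about 1 point for five patients and at most 1.7 for an average site. The failures-only scenario describes misuse, since a recorded failure is not missing, and the 10% and 20% centres are assumed. All the figures concern a secondary outcome in the smallest subgroup. Several disclosure duties also apply: SAP section 3 asks for discrepancies from the protocol to be explained, SAP 8.4 provides for a listing of unresolved data, and Protocol section 15 requires later deviations to be summarised in the study report. Site-level data-quality criteria might also sit in the monitoring or data management plans, which were not supplied.

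Much of this limits the size of the problem, and it is fair that the SAP 8.1.1 and early-leaver conflicts are secondary: the first speaks of available data, and the second covers only early leavers. The core remains. Words such as several, or one entire centre, are not a threshold, and a centre may be large. Disclosure and approval do not say when exclusion is justified. SAP 8.5 addresses changes to the plan, and an exclusion that SAP 8.6 already allows is not clearly a change. The departure from Protocol 15.1 is not explained where it occurs. Reading the clause as ordinary per-table missingness does not work either, because it allows a whole centre to be removed. Criteria in an unsupplied plan would still leave SAP 8.6 contradicting itself.

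**Conclusion.** The concern holds and should be fixed. SAP 8.6 contradicts itself and also conflicts with Protocol 15.1 and 15.2.2. The supplied text contains no criterion, quantified limit or timing rule for using the permission. No claim is made about the SAP pages that were not supplied.

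The expected numerical effect is modest: within about 1.7 points for an average site, against a half-width of 5.7 to 5.8. It approaches or exceeds that half-width only if exclusion is selective or the centre is large and atypical. Those cases rest on assumed centre sizes and failure rates, which the documents neither support nor rule out. Effects on the primary treatment-pattern tables were not quantified. They are exposed too, since an average site holds 2000/35 ≈ 57 patients and SAP 8.1.2 allows combinations seen in fewer than 25 subjects to be dropped.

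**What to change.** Delete the last sentence of SAP 8.6. Keep every consented patient in the Full Analysis Set apart from the inclusion-violation rule already stated, and show missing counts in each table as planned.

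If removal of a patient or centre for documented data-integrity failure must remain possible, replace the sentence with:

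- objective criteria, fixed before the final results are seen and applied without reference to treatment or outcome;
- a record of sponsor approval under SAP 8.5, since the revised permission would itself be a plan change that departs from the protocol;
- a report of each exclusion with its reason;
- the main tables with and without the excluded data, with the SAP naming which tables these are (at least the treatment-combination distributions and the failure percentages).

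The cost is one sentence deleted or replaced. If an exclusion occurs, its reason is reported and the named tables are run a second time. No new data are needed.

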### **8.7 Interim analysis**

Two interim analyses are planned – in 2019 and 2020 – with corresponding interim data locks for the completed cases:

- 2019: about 700 completed cases for retrospective data analysis
- 2020^2: 3000 completed cases for retrospective and partial prospective data (up to 6 months)

---

 According to the current version of the protocol, the set of collected data has been reduced to 2000 cases. Therefore, the second analysis (second look) of data was not performed in 2020.

Protocol ID	MACS-2017-102279	STATISTICAL ANALYSIS PLAN	Page 30 of 41	
IP	N/A		Date	30.12.2021
ID	MACS-2017-102279_SAP		Version	v1.2 final

All cases will be included into interim analysis with the prerequisite of complete data cleaning, i.e., corresponding eCRF forms are complete, free of any pending queries and signed by the corresponding investigator.

Retrospective data analysis (2019): will include the following endpoints (all endpoints will be assessed retrospectively for the period of 2 years of retrospective data collection):

- 1) Treatment patterns associated with prior biologic agents use or non- biological therapy according to the algorithm provided in the section 8.1.2);
- 2) Demographic data, medical history, treatment history, concurrent diseases, concomitant medications by treatment group/pattern;
- 3) Demographic data for FAS;
- 4) Family history of IBD, smoking habits, medical history comorbidities for FAS;
- 5) Disease characteristics: age of disease onset, location of disease, clinical course, disease severity, intestinal and systemic (extraintestinal) manifestations, complications in history for FAS;
- 6) Frequency and methods of assessment of UC/CD disease activity;
- 7) Assessment of healthcare resource utilization;
- 8) TB incidence and prevalence in IBD patients by treatment pattern;
- 9) TB medication's use in IBD patients by treatment pattern;
- 10) Compliance between the assessment of IBD status by investigator and objective methods of assessment (Mayo index, Harvey-Bradshaw index, instrumental assessments).

No safety analysis will be performed for the retrospective data analysis as there will be no safety data in the retrospective part of the study.

Retrospective and partial prospective data analysis (2020): will include the following endpoints (main endpoints will be assessed retrospectively for the period of 2 years of retrospective data collection and for the 6 months of the prospective data collection; safety endpoints will be assessed for prospective part of the study only):

- 1) Treatment patterns associated with prior biologic agents use or non-biological therapy according to the algorithm provided in the section 8.1.2);
- 2) Demographic data, medical history, treatment history, concurrent diseases, concomitant medications by treatment group/pattern;
- 3) Frequencies and time to achieve remissions and exacerbations by treatment group/pattern;
- 4) Frequency and methods of assessment of UC/CD disease activity;
- 5) Assessment of healthcare resource utilization;

Protocol ID	MACS-2017-102279	STATISTICAL ANALYSIS PLAN	Page 31 of 41	
IP	N/A		Date	30.12.2021
ID	MACS-2017-102279_SAP		Version	v1.2 final

- 6) Probable causes preventing achieving T2T targets during routine care;
- 7) The extent to which proposed Treat to Target goals are achieved by treatment group/pattern;
- 8) TB incidence and prevalence in IBD patients by treatment pattern;
- 9) TB medication's use in IBD patients by treatment pattern;
- 10) Adverse drug reactions (ADRs) on IBD treatments;
- 11) Adverse events on Entivyo® (vedolizumab) treatment;
- 12) Serious adverse events on IBD treatments (including Entivyo® (vedolizumab) treatment).

As there are no statistical hypotheses tested, there will be no alpha spending function correction applied to the interim analysis.

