4.3 IBD activity assessment

Validated Mayo score evaluates ulcerative colitis stage, based on four parameters (full Mayo score): stool frequency, rectal bleeding, endoscopic evaluation and physician's global assessment (see **Appendix 3**). Each parameter of the score ranges from zero (normal or inactive disease) to 3 (severe activity). The partial Mayo score uses the three non-invasive components of the full Mayo Score (stool frequency, rectal bleeding and Physician's global assessment). This excludes the score for the endoscopic findings; therefore, the maximum score is reduced from 12 to 9 points. The full or partial Mayo score (in accordance with routine clinical practice) will be evaluated at each study visit.

Harvey-Bradshaw index (HBI) is used in the assessment of Crohn's disease activity (see **Appendix 4**). It is a validated clinical index for CD, including the 5 categories of: general well-being, abdominal pain, number of liquid stools, abdominal mass and complications. The score ranges from 0 to 25 with higher scores indicating higher disease activity. The scores were classified as follows: less than 5 is remission, 5 to 7 is mild, 8 to 16 is moderate, and greater than 16 is severe. HBI will be evaluated at each study visit.

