Appendix 3. Mayo score

The full Mayo Score evaluates ulcerative colitis stage, based on four parameters: stool frequency, rectal bleeding, endoscopic evaluation and Physician's global assessment (1,2). Each parameter of the score ranges from zero (normal or inactive disease) to 3 (severe activity). The following table indicates, for each parameter, the input values with their respective scores.

Parameter	Clinical evaluation (single choice)	Score
1. Stool frequency (per day)	
 normal number of stools 1-2 more than normal 3-4 more than normal ≥ 5 more than normal 	0 1 2 3
2. Rectal bleeding (indicate the most severe bleeding of the day)	
 none streaks of blood with stool in less than half of the cases obvious blood with stools in most cases blood alone passes 	0 1 2 3
3. Endoscopic findings	
 normal mucosa or inactive disease mild activity (erythema, decreased vascular pattern, mild friability) moderate activity (marked erythema, lack of vascular pattern, friability, erosions) severe activity (spontaneous bleeding, large ulcerations) 	0 1 2 3
4. Physician's global assessment	
 normal mild disease moderate disease severe disease 	0 1 2 3

Calculation formula: sum of the scores of the four parameters.

Score	Decoding
0 - 2	Remission (provided that no subscore for each single parameter is greater than 1)
3 - 5	mild activity
6 - 10	moderate activity
> 10	severe activity

Partial Mayo Score uses the three non-invasive components of the full Mayo Score (stool frequency, rectal bleeding and Physician's global assessment). This excludes the score for the endoscopic findings, therefore the maximum score is reduced from 12 to 9 points (1,2). This simplified index maintains a good relationship with the full Mayo Score in identifying clinical response as perceived by patients (3).

Score	Decoding
<2	remission
2 - 4	mild activity
5 - 7	moderate activity
> 7	severe activity

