### 5.3.1 *Data collected on the Baseline visit (V1), including collection of Retrospective data within two years before of patient enrolment in the study*

The baseline visit takes place at the physician's office. Data to be collected:

- Date of Informed consent form signing (day, month, year);
- Inclusion/exclusion criteria;
- Date of visit (day, month, year);
- Demographics data (gender, date of birth, ethnicity, region of residence, smoking status, employment status (employed, unemployed, retired, student, other));
- Disability:
  - Disability group
  - Cause of disability
  - Year of disability

Protocol ID	MACS-2017-102279	STATISTICAL ANALYSIS PLAN	Page 11 of 41	
IP	N/A		Date	30.12.2021
ID	MACS-2017-102279_SAP		Version	v1.2 final

- Physical examination: height (cm) and weight (kg), body mass index calculation;
- Medical history/Concurrent medical conditions (disease, date of diagnosis, resolution date);
- History of inflammatory bowel disease (IBD):
  - Type of inflammatory bowel disease (ulcerative colitis (UC) or Crohn's disease (CD));
  - Date of IBD diagnosis;
  - Date of IBD symptoms onset;
  - Availability of observation in the current investigational site within previous 2 years;
- IBD family history (degree of relationship);
- Clinical course of IBD (acute, chronic continuous, chronic recurrent);
- IBD assessment for the last 2 years and at the time of the baseline visit:
  - Disease extent according to the following Montreal Classification categories;
  - Systemic (extra intestinal) IBD manifestations;
  - IBD complications;
  - Vaccination in accordance with IBD treatment guidelines.
- Disease activity data at baseline visit will consist of specified signs and symptoms depending on the disease type:
  - CD: abdominal pain severity, number of liquid stools per day, presence of an abdominal mass, endoscopic findings (if done), documented presence of CD complications, and Harvey Bradshaw Index or other documented disease activity scales (if applicable);
  - UC: frequency of stools/day, rectal bleeding, endoscopic findings (if done), physician global assessment of disease severity, and Mayo scores or other documented disease activity scales (if applicable).
- IBD status at baseline visit:
  - IBD status as judged by investigator (remission, incomplete remission, flare, others), nature of remission at the time of examination;
  - IBD flare(s).

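### In UC, the Mayo index is not an independent check on the investigator's disease status, because it contains the physician's global assessment

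*SAP*

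**What the plan says.** Among the endpoints of the 2019 retrospective interim, SAP 8.7 item 10 lists "Compliance between the assessment of IBD status by investigator and objective methods of assessment (Mayo index, Harvey-Bradshaw index, instrumental assessments". It names no agreement statistic and no cut-off, and it does not say that any Mayo item is left out.

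The judgement being checked is described in SAP 5.3.1 as "IBD status as judged by investigator (remission, incomplete remission, flare, others), nature of remission at the time of examination". The same section lists, under a separate heading for disease activity, "UC: frequency of stools/day, rectal bleeding, endoscopic findings (if done), physician global assessment of disease severity". SAP 5.3.2 repeats both fields for Visits 2 and 3.

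Protocol 4.3 explains that "The partial Mayo score uses the three non-invasive components of the full Mayo Score". Those three are stool frequency, rectal bleeding and PGA; the full score adds endoscopy. Appendix 3 scores each item 0 to 3. It sets partial Mayo remission at a total below 2, and full Mayo remission at a total of 0 to 2 with no single item above 1. Either version may be used, according to routine practice. The Harvey-Bradshaw index for CD has five items, none of them a physician's global rating.

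**The concern.** A check of a physician's judgement needs a reference that does not contain that judgement. Here the UC reference includes the physician's own global rating of severity, listed for the same visit as the status it is meant to test. This is incorporation bias: some of the agreement comes from the overlap and not from the patient's symptoms or mucosa.

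At stake is how a reader interprets the UC agreement figure. Good agreement with an index labelled objective would be taken as evidence that investigators' status calls are borne out by independent findings. Part of that evidence would be the physician agreeing with a related rating of their own, and the report would not show how much.

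**Working it through.** **1. The documents' own figures.** Four items × 3 = 12 and three items × 3 = 9, matching the maxima in Protocol 4.3. PGA can contribute 3/12 = 25% of the full and 3/9 = 33% of the partial maximum.

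**2. What Appendix 3 forces.**
- PGA of 2 or 3: the partial total is at least 2, so it is not below 2; the full score has an item above 1. Remission is impossible on either version, whatever the stools and bleeding.
- PGA of 1: partial remission needs stool = bleeding = 0.
- PGA of 0: partial remission still needs stool + bleeding ≤ 1, so it is not guaranteed.

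Only the active direction is forced. This step needs no assumptions.

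**3. Size when the symptoms carry no information.** Let m be the share judged in remission, q = P(stool + bleeding ≤ 1), r = P(stool = bleeding = 0), and a = P(PGA = 1) among those not in remission. Assume that stool and bleeding are independent of the judgement and of each other, that PGA = 0 when the investigator says remission, and that PGA is 1 to 3 otherwise. Then, for partial Mayo:

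- agreement = m·q + (1 − m)(1 − a·r)
- share in Mayo remission, M = m·q + (1 − m)·a·r
- chance agreement = m·M + (1 − m)(1 − M)
- agreement − chance = 2m(1 − m)(q − a·r), which is positive because q exceeds a·r
- kappa = (agreement − chance)/(1 − chance)

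With PGA removed and the same cut-off kept, agreement = m·q + (1 − m)(1 − q), which equals chance, so kappa = 0.

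The documents give none of m, q, r or a. The assumed values are m = 20, 30, 50 or 70%; P(0, 1, 2, 3) for each subscore as in the table; and PGA 1/2/3 among the rest as equal thirds, 0/.5/.5 or .6/.3/.1. That makes 4 × 4 × 3 = 48 combinations. Selected partial Mayo results:

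| Subscore P(0,1,2,3) | q | r | m | a | Agreement | Kappa |
|---|---|---|---|---|---|---|
| .10/.20/.40/.30 | .05 | .01 | .7 | .6 | 33% | 0.03 |
| .25 each | .1875 | .0625 | .5 | 1/3 | 58% | 0.17 |
| .50/.25/.15/.10 | .50 | .25 | .5 | 1/3 | 71% | 0.42 |
| .50/.25/.15/.10 | .50 | .25 | .5 | 0 | 75% | 0.50 |
| .70/.20/.07/.03 | .77 | .49 | .2 | 0 | 95% | 0.84 |

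Second row in full: agreement = .5 × .1875 + .5 × (1 − .0208) = .583. At m = .5 chance is .5, so kappa = .083/.5 = 0.17.

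Last row: agreement = .2 × .77 + .8 = .954; M = .154; chance = .2 × .154 + .8 × .846 = .708; kappa = .246/.292 = 0.84.

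Across all 48 combinations, partial Mayo agreement is 33–95% and kappa 0.03–0.84. For full Mayo, with endoscopy also unrelated, they are 31–94% and 0.01–0.80.

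**4. Which values can enter.** The visit tables mark disease activity data and IBD status from Visit 1 onward, with nothing in the retrospective column. Although item 10 belongs to the retrospective interim, the Mayo comparison can use only baseline values.

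**The case against.** The strongest reply is that the overlap is partial and the item is minor. PGA is a quarter to a third of the score. It is a severity rating on a separate field from IBD status, with different categories, and the documents do not equate the two. Item 10 carries no test and no decision. It appears in the 2019 list only, and not among the primary or secondary endpoints. The SAP sets no remission cut-off or kappa for it, so the two-category table used above is a reviewer's construction from four status categories. All of this stands, and it limits the point to an inflation of unknown size in one descriptive table.

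Four stronger readings are tempting, and the documents do not support them.

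- *Agreement is high by construction.* Under the assumptions above it can be poor or high; kappa near 0.8 needs mostly normal subscores and every non-remission patient at PGA 2 or more.
- *The check cannot reveal an over-called flare, or will look good regardless.* A flare scored PGA 1 with normal stools and no bleeding has a partial Mayo of 1, which is remission, so it shows as discordant. Investigator remission with stool plus bleeding of 2 or more also shows. Instrumental assessments are a separate comparator within item 10, where done.
- *Treat-to-target results are compromised.* SAP 8.1.3 draws on investigator feedback and objective methods, but it does not refer to item 10 or to total Mayo. The UC targets in Protocol 4.4 rest on bleeding, bowel habit and the endoscopic subscore, not PGA.
- *UC and CD agreement are being wrongly compared.* Harvey-Bradshaw has no PGA item, so the two figures would mean different things, but the plan presents UC and CD separately and item 10 proposes no contrast.

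**Conclusion.** The point holds in limited form. For UC, item 10 uses as an objective reference an index that includes a closely related physician judgement. Agreement is inflated in one direction: a flare with PGA of 2 or more always counts as agreement. That much follows from Appendix 3 alone.

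The size of the inflation cannot be known from the documents. The kappa range of about 0.03 to 0.84 for partial Mayo, against 0 without PGA, rests on assumed subscore distributions and remission shares, on collapsing status to remission or not, and on PGA following the judgement completely. That last assumption is the worst case for overlap, so a looser link would not enlarge the inflation on that account. The primary outcome, the treat-to-target definitions and the CD comparison are unaffected. This is a desirable correction, not an essential one.

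**What to change.** For item 10, and for any report that cites it:

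- Compare UC investigator status with stool frequency and rectal bleeding without PGA, stating the cut-off used. Add the endoscopic subscore and CRP or calprotectin where done.
- Show both discordant cells: flare by investigator with normal non-PGA items, and remission by investigator with active ones.
- If agreement with total Mayo is also shown, do not label it objective, and note that it contains PGA.

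Stool frequency, bleeding and endoscopic findings (if done) are already listed at each visit in SAP 5.3.1 and 5.3.2, and the biomarkers in Protocol 12.7, so no new data are needed. The cost is SAP wording and one re-run table. SAP v1.2 postdates an interim analysis, so the change may mean revising a table already produced. Reported UC agreement will probably be lower, and endoscopy and biomarker comparisons will cover only patients who had those tests in routine practice.
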